### Primary Outcome:

- Hospital length of stay (days)

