### Secondary Outcomes (Clinical Metrics):

- Mortality
- Incidence of respiratory failure requiring mechanical ventilation > 24 hours
- Incidence of tracheostomy
- Inpatient incidence of pneumonia
  - >10,000 cfu/mL on bronchioalveolar lavage -or-
  - Clinical diagnosis of pneumonia with subsequent antibiotic treatment
- Utilization of regional anesthesia (binary outcome)
- Opioid usage (continuous and binary)
- Lengths of stay
  - Hospital-free days (= 30 minus number of hospital days; in-hospital death = 0)
  - Ventilator-free days (= 30 minus number of ventilator days; in-hospital death = 0)

- ICU-free days (= 30 minus number of intensive care unit days; in-hospital death = 0)
- Re-intervention rates for surgical complications, including bleeding, seroma, and surgical site infection

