### Data Collection

The clinical research staff will follow the subjects throughout their hospitalization (or up to 30 days, whichever comes first) for complications such as surgical site infections, pneumonia, need for reoperative procedures and other complications commonly associated with rib fractures.

The data will be reviewed and entered into the UT Redcap database. Each subject will be assigned a study specific number. The subject's medical record and the MHH-TMC trauma registry will be utilized for data collection purposes. Data will be collected until discharge or 30 days (whichever occurs first) and questionnaires will be conducted up to 6 months post ED admission.

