### Sample Size Calculation

We expect to enroll 150-250 total patients. We calculated the effect size we will be able to detect in hospital LOS, assuming a median LOS of 10 days (IQR 6-15) in the control group and two-sided alpha of 0.05. A sample size of 150 patients (75 per group) will provide 85% power to detect a difference of 3 days (*i.e.*, median LOS of 7 days in intervention group). With a sample size of 250 patients, we will have 89% power to detect a difference of 2.5 days in hospital LOS.

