### Frequentist Analysis

Generalized linear models (GLMs) will be used to analyze all outcomes and will include treatment group and unit of admission (stratifying variable) as covariates. For LOS outcomes, negative binomial or zero-inflated negative binomial (for outcomes with large number of zeros; *e.g.*, ventilator days, ICU days) regression models will be used. Binary outcomes will be analyzed with log binomial regression models to estimate relative risks (RRs). For longitudinal outcomes, we will use mixed models including treatment group, time, and center as covariates and a random intercept (and slope if needed) for subject. We will report RRs or group differences and 95% confidence intervals for all outcomes.

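### Pneumonia is counted only until discharge, so if SSRF shortens hospital stay its relative risk is pushed below 1 without any true effect on pneumonia

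*Combined protocol and SAP*

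**What the plan says.** Under Secondary Outcomes (Clinical Metrics) the endpoint is "Inpatient incidence of pneumonia". It is met by a quantitative lavage culture or by "Clinical diagnosis of pneumonia with subsequent antibiotic treatment".

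The Data Collection section follows subjects "throughout their hospitalization (or up to 30 days, whichever comes first) for complications such as surgical site infections, pneumonia" and other complications. It then sets the general rule: "Data will be collected until discharge or 30 days (whichever occurs first) and questionnaires will be conducted up to 6 months post ED admission". The questionnaire in Appendix A covers EQ-5D-5L, return to work or activity, and rib pain. It has no item on pneumonia or readmission.

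Frequentist Analysis assigns binary outcomes to log binomial regression, with treatment group and unit of admission as covariates. It mentions no offset, fixed time point, time-to-event analysis or sensitivity analysis for unequal follow-up. Bayesian Analysis reuses the same models.

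Hospital length of stay (LOS) is the primary outcome. Sample Size Calculation works from "assuming a median LOS of 10 days (IQR 6-15) in the control group and two-sided alpha of 0.05" and states: "A sample size of 150 patients (75 per group) will provide 85% power to detect a difference of 3 days". For 250 patients it gives 89% power for 2.5 days.

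**The concern.** For anyone discharged before day 30, the period in which a pneumonia can be counted is the hospital stay itself. A treatment that shortens stay also shortens that period. A pneumonia starting on day 9 counts in a control patient still in hospital. The same pneumonia in an SSRF patient who left on day 7 does not count, even if it leads to readmission.

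A single effect on stay could then be reported as two: a shorter stay and fewer pneumonias. The Abstract names pneumonia among the endpoints without the inpatient qualifier, and the Background cites less pneumonia as a benefit seen in earlier flail-segment trials. An RR below 1 is therefore likely to be read as prevention. The reported Bayesian probabilities of benefit would carry the same bias.

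**Working it through.** **Inputs from the documents.** Control LOS median 10 days, IQR 6–15; SSRF median 7 days (150 patients) or 10 − 2.5 = 7.5 days (250 patients); 1:1 allocation; capture ends at discharge or day 30.

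**Assumed, because the documents do not give them.** Pneumonia rate, onset timing, and how risk relates to LOS.

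**1. The plan's own power figures.** The plan names no formula. A negative binomial with mean 11.4 and k = 2.5 fits the stated median and IQR. A Wald test on the log ratio has SE = √{[(1/μ₁ + 1/k) + (1/μ₂ + 1/k)]/n}.
- 75 per arm, ratio 0.70: μ₂ = 7.98, SE = √(1.013/75) = 0.116, z = 0.357/0.116 = 3.07, power = Φ(3.07 − 1.96) = 86.6% (stated 85%).
- 125 per arm, ratio 0.75: μ₂ = 8.55, SE = √(1.005/125) = 0.0897, z = 0.288/0.0897 = 3.21, power = 89.4% (stated 89%).

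The stated figures are reproduced to within two points, so the LOS inputs can be used as they stand.

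**2. Share of 30-day pneumonias counted, with no true effect.** Take LOS as log-normal: L = median × exp(0.679 z), where 0.679 = ln(15/6)/(2 × 0.6745) and z is standard normal. Let onset be exponential with mean m, cut at day 30. A patient with stay L has counted share

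F(L) = [1 − exp(−min(L,30)/m)] / [1 − exp(−30/m)].

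Weight F(L) by the patient's pneumonia risk and average over z. Risk and onset are identical in the two arms, so the true RR is 1. The apparent RR is the SSRF share divided by the control share.

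Risk independent of LOS:

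| Mean onset (days) | Control share | SSRF share (median 7) | RR, median 7 | RR, median 7.5 |
|---|---|---|---|---|
| 3 | 0.915 | 0.852 | 0.93 | 0.95 |
| 5 | 0.820 | 0.727 | 0.89 | 0.91 |
| 7 | 0.741 | 0.636 | 0.86 | 0.89 |
| 10 | 0.658 | 0.545 | 0.83 | 0.86 |

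**3. Risk rising with LOS.** Patients who leave early are probably at lower risk. Let logit(risk) = −1.5 + b·z, with b = 1 or 2 per SD of log LOS (assumed).

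| Mean onset (days) | b = 1, median 7 | b = 2, median 7 | b = 1, median 7.5 | b = 2, median 7.5 |
|---|---|---|---|---|
| 3 | 0.96 | 0.98 | 0.97 | 0.98 |
| 5 | 0.93 | 0.94 | 0.94 | 0.95 |
| 7 | 0.90 | 0.91 | 0.92 | 0.93 |
| 10 | 0.87 | 0.88 | 0.89 | 0.90 |

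The direction holds but the bias is smaller. If pneumonia itself prolongs the stay, which is not modelled here, it shrinks further.

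**4. More extreme inputs, risk independent of LOS.** A constant onset rate to day 30 gives 0.71–0.77 (3 days) or 0.76–0.81 (2.5 days). Cutting every stay by 3 days instead of proportionally gives 0.81–0.87 for mean onset 2–7 days. That version leaves Φ(ln(3/10)/0.679) = Φ(−1.77), about 4% of patients, with no stay at all. I do not rest the point on either.

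**5. Effect on inference.** Assume a 15% true 30-day risk, mean onset 5 days, 75 per arm and risk independent of LOS. Counted proportions are 0.15 × 0.820 = 0.1229 and 0.15 × 0.727 = 0.1091. The difference is 0.0138, with SE = √[(0.1229 × 0.8771 + 0.1091 × 0.8909)/75] = 0.0523. The chance of a falsely significant result favouring SSRF is Φ(0.0138/0.0523 − 1.96) = 4.5%, against a nominal 2.5%. Over mean onsets of 3 to 10 days, the same formula gives about 4–6% at either sample size with its matching LOS difference. With an assumed 30% risk and five-day onset (24.6% against 21.8%) it is 6%.

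**The case against.** The best defence has four parts.

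- **The label is open.** The endpoint is called inpatient, and a 30-day window is partly a different estimand. This stands as far as it goes, but a label does not equalise the windows, and the Abstract drops it.
- **The shift is small against the noise.** With SE(log RR) = √[2(1 − p)/(np)], the 95% interval around RR 1.0 is 0.47–2.14 for p = 15% and 75 per arm, and 0.65–1.54 for p = 25% and 125 per arm. A null RR of 0.9 lies well inside both. This stands: the point concerns a secondary outcome and is modest in size. The bias nonetheless has a known direction if SSRF shortens stay.
- **The inputs are assumed.** This stands. If most pneumonia begins in the first days, or in patients who stay long anyway, the RR is close to 1.
- **The remedy has its own bias.** The Limitations section says that those administering the questionnaire are not blinded, and patients know whether they were operated on. A telephone report cannot supply a lavage culture. This stands and shapes the fix.

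Two stronger readings are tempting. A reader might infer that the trial itself predicts a shorter stay with SSRF, so that the bias is built in. The Hypothesis section names opioid use, health status, return to work or activity, and pain resolution, not LOS. The 3 and 2.5 days are differences the trial could detect, not forecasts. A reader might also extend the point to DVT and PE. Both are only data elements in Appendix B and not listed outcomes, so the plan specifies no comparison between arms for them.

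**Conclusion.** The point holds as a conditional one about pneumonia. As written, the plan makes the pneumonia counting window depend on the primary outcome and does not correct for it. If SSRF shortens stay, the RR moves below 1 with no true effect; if stays are equal, there is no bias.

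At the plan's detectable differences, with assumed mean onset of 3 to 10 days and proportionally shorter stays, the null RR is about 0.83–0.95 when risk is independent of LOS and about 0.87–0.98 when risk rises with LOS. The second range is the more plausible, because independence enlarges the figure. The primary outcome is unaffected.

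The documents do not support saying that an observed pneumonia benefit would be an artefact. They support saying that the planned analysis could not separate a modest benefit from a shorter window.

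**What to change.** - **Secondary Outcomes (Clinical Metrics):** define pneumonia as occurring within 30 days of ED admission in both arms. Keep the in-hospital count as a supplementary result, described as in-hospital.
- **Data Collection:** follow pneumonia to day 30 whatever the discharge date, from the medical record (already a data source), including readmissions.
- **Appendix A:** add one question at the existing 30-day contact, for example whether the patient has been treated with antibiotics for pneumonia since discharge, and when. Confirm reported events against records where possible.
- **Appendix B:** add a pneumonia item with onset date that applies to both arms. The present items are worded relative to SSRF.

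**Cost:** protocol wording, one question on a contact already planned for every subject, and a record check. No new visit is needed.

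**Downside:** events treated elsewhere rest on unblinded patient report that cannot supply lavage results, and patients not reached at 30 days contribute record data only. Showing the 30-day and in-hospital results side by side, with the number of events resting on report alone, lets readers judge both. The change needs to be prospective, since post-discharge events that were never asked about cannot be reliably recovered later.

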#### Appendix B. List of Data Elements to be Collected

Study number

Gender (male/female)

Age

Race (white, black, Hispanic, Asian, other, unknown)

Trauma type (blunt/penetrating)

Mechanism (MVC, MCC, fall, auto pedestrian, ATV, assault, crush, GSW, stab, other)

Date/time of injury

PH vital signs

Transfer? (yes/no)

ED arrival date/time

ED vitals

ED CBC

ED BMP

ED rTEG

ED lactate

ED base excess

Unit of admission

Randomization group (SSRF/usual care)

R 1st rib fx?

Segmental?

Displaced?

R 2nd rib fx?

Segmental?

Displaced?

R 3rd rib fx?

Segmental?

Displaced?

R 4th rib fx?

Segmental?

Displaced?

R 5th rib fx?

Segmental?

Displaced?

R 6th rib fx?

Segmental?

Displaced?

R 7th rib fx?

Segmental?

Displaced?

L 1st rib fx?

Segmental?

Displaced?

L 2nd rib fx?

Segmental?

Displaced?

L 3rd rib fx?

Segmental?

Displaced?

L 4th rib fx?

Segmental?

Displaced?

L 5th rib fx?

Segmental?

Displaced?

L 6th rib fx?

Segmental?

Displaced?

L 7th rib fx?

Segmental?

Displaced?

Radiographic flail segment? (yes/no)

Flail chest? (yes/no)

Right clavicle fx? (yes/no)

Left clavicle fx? (yes/no)

Right scapula fx? (yes/no)

Left scapula fx? (yes/no)

Mechanical ventilation immediately prior to SSRF? (yes/no)

Tracheostomy prior to SSRF? (yes/no)

Clinical suspicion of PNA prior to SSRF? (yes/no)

Chest tube prior to SSRF? (yes/no)

Date/time of SSRF

Time from admission to SSRF (hours)

Procedure time (min)

Hardware system (Synthes/KLS Martin)

Right ribs stabilized by SSRF

1 (yes/no)

2 (yes/no)

3 (yes/no)

...

Left ribs stabilized by SSRF

1 (yes/no)

2 (yes/no)

3 (yes/no)

...

VATS? (yes/no)

Thoracotomy? (yes/no)

w-RTS

ISS

AIS head/neck

AIS face

AIS chest

AIS abdomen

AIS extremity

AIS external

Regional analgesia for rib fxs? (yes/no)

If yes, what kind? (epidural, paravertebral, intercostal, serratus plane, other)

Post-SSRF PNA? (yes/no)

Post-SSRF hardware infection? (yes/no)

Post-SSRF seroma requiring intervention? (yes/no)

Post-SSRF hematoma requiring intervention? (yes/no)

Post-SSRF hardware failure? (yes/no)

Post-SSRF need for hardware removal for any reason? (yes/no)

Post-SSRF SSI? (yes/no)

Superficial? (yes/no)

Deep? (yes/no)

Organ space? (yes/no)

DVT? (yes/no)

PE? (yes/no)

Discharge date/time

Discharge disposition (home, rehab, SNF, LTAC, transfer to other hospital, level 1 psych, morgue, other)

Total opioid use (MME)

MME/day

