Opioid prescription at discharge? (yes/no)

Tramadol prescription at discharge? (yes/no)

Ventilator days

ICU days

Hospital days

Did the patient survive to 1 month? (yes/no)  
Was the patient able to answer questions at 1 month? (yes/no)  
Did the patient consent to be asked questions at 1 month? (yes/no)

Did the patient survive to 3 months? (yes/no)  
Was the patient able to answer questions at 3 months? (yes/no)  
Did the patient consent to be asked questions at 3 months? (yes/no)

Did the patient survive to 6 months? (yes/no)  
Was the patient able to answer questions at 6 months? (yes/no)  
Did the patient consent to be asked questions at 6 months? (yes/no)

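### The 30-day free-day scores are zero only for death in hospital and stop counting at discharge, so early post-discharge deaths and patients transferred on a ventilator are credited with free days

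*Combined protocol and SAP*

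**What the plan says.** Secondary Outcomes (Clinical Metrics) defines three scores on a 30-day scale. The one for ventilation reads "Ventilator-free days (= 30 minus number of ventilator days; in-hospital death = 0"). The scores for the hospital stay and for intensive care have the same form: each subtracts the days counted from 30, and each gives 0 only to a patient who dies before leaving hospital.

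The Data Collection section closes the window for clinical data: "Data will be collected until discharge or 30 days (whichever occurs first"). The sources it names are this hospital's record of the patient and its own trauma registry. After discharge, only the questionnaires at 30 days, 3 months and 6 months follow.

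Appendix B expects patients to leave for other facilities: "Discharge disposition (home, rehab, SNF, LTAC, transfer to other hospital, level 1 psych, morgue, other"). It has one field each for ventilator, ICU and hospital days. It has no field for ventilation at discharge, readmission, or days in a receiving facility. It does ask "Did the patient survive to 1 month? (yes/no"), but nothing links that answer to the three scores. Mortality is listed as a separate secondary outcome, without a time point.

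**The concern.** A free-day score combines survival and duration over a fixed window, so that death or continued dependence cannot look like a short stay. Here the window is 30 days, but the death rule and the counting both end when the patient leaves hospital. Two kinds of patient are then mis-scored: those who die between discharge and day 30, and those who leave on a ventilator.

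The Abstract and Background name mortality, prolonged ventilation and tracheostomy among the burdens that surgery might reduce. If patients with these outcomes are more frequent in one arm, the scores understate that arm's burden. Depending on the arm, this could mask a benefit or a harm of surgery.

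**Working it through.** **The plan's own figure.** The documents compute power only for the primary outcome, hospital length of stay: 85% with 75 per arm (10 against 7 days) and 89% with 250 patients in total (a 2.5-day difference). The Sample Size Calculation rests on this input: "assuming a median LOS of 10 days (IQR 6-15) in the control group and two-sided alpha of 0.05". It does not name the method. A negative binomial distribution fitted to those quartiles has mean m = 11.4 and size k = 2.5. With ratio r, n per arm and Var(log ratio) = (1/m + 1/k + 1/(m r) + 1/k)/n:

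- n = 75, r = 0.70: variance 1.013/75 = 0.01351, SE 0.1162, z = 0.357/0.1162 - 1.96 = 1.11, power 86.6%.
- n = 125, r = 0.75: variance 1.005/125 = 0.00804, SE 0.0897, z = 0.288/0.0897 - 1.96 = 1.25, power 89.4%.

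Both are within 2 points of the stated values. Other methods gave 76.8% to 89.5% and 82.5% to 91.7%. None of this involves the free-day scores, so the point below leaves the power statement untouched.

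**Scoring patients by the written rule.** Formula: score = 30 - days counted; 0 only if the death is in hospital. The patients are illustrations.

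1. Discharged on day 10, dies on day 20. Hospital-free days: 30 - 10 = 20. A survivor discharged on day 10 also scores 20. If this patient had 3 ventilator days and 4 ICU days, the other scores are 27 and 26. Under a rule that gives 0 for any death by day 30, all three scores are 0.
2. Ventilated on days 1 to 14, transferred on day 14 still ventilated. Ventilator-free days: 30 - 14 = 16. A patient liberated on day 14 also scores 16. If ventilation in fact continues to day 30, the true score is 30 - 30 = 0, an error of 16 days.

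**Possible effect on the comparison.** The documents give no rate for ventilated transfer or post-discharge death, so the rates are assumed. Shift in the mean difference = excess proportion in one arm x days wrongly credited per patient. A transfer between day 12 and day 18, with ventilation to day 30, wrongly credits 18 down to 12 days.

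| Assumed excess | 12 days each | 18 days each |
|---|---|---|
| 2 points | 0.24 | 0.36 |
| 3 points | 0.36 | 0.54 |
| 5 points | 0.60 | 0.90 |

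With 75 per arm, 2 to 5 points is 1.5 to 3.75 patients. For post-discharge deaths like patient 1, each point of excess shifts mean hospital-free days by 0.01 x 20 = 0.20. These are shifts in plain means; the planned negative binomial models would express them as ratios.

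**The case against.** **These patients are not lost to the trial.** This is correct. Ventilation beyond 24 hours, tracheostomy and mortality are separate outcomes, survival is asked at 1, 3 and 6 months, and health status is measured at 30 days. The weakness is confined to three summary scores.

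**The formulas do not say that only days in this hospital count.** Also correct. That reading follows from the end of data collection at discharge, the named sources, and the absence of any field for later days. The zero for death needs no such inference: it is explicitly limited to deaths in hospital.

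**The effect may be small against noise.** If the control interquartile range for length of stay (6 to 15) is treated as roughly normal and borrowed for ventilator-free days, the SD is 9/1.349 = 6.67. The standard error of a mean difference at 75 per arm is then 6.67 x sqrt(2/75) = 1.09 days. Shifts of 0.24 to 0.90 days are about 0.2 to 0.8 of that. This stands, and it limits the weight of the point.

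**Stronger readings that the documents do not support:**

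- That such patients score as fully recovered. Days before discharge are still deducted. A patient who goes home well on day 14 ties with the day-14 transfer on hospital-free days (16), but not in general on ventilator-free days: he scores 25 after 5 ventilator days and 30 if never ventilated.
- That the scores favour usual care. This needs an excess of such patients among controls, and no figure in the documents shows one.
- That the primary outcome is mis-scored. Hospital length of stay ends at discharge by definition, and the plan does not present it as recovery.
- That later days should simply be added from the 30-day call. That would bring recall collected by unblinded staff into scores based on records. Appendix B already expects that some patients cannot or will not answer.

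**Conclusion.** The point holds for the scoring rule. As written, all three scores treat a death between discharge and day 30 as survival, and the ventilator-free score credits free days to a patient who left on a ventilator. The error for one patient is large: 20 hospital-free days and 16 ventilator-free days in the two examples.

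The consequence for the comparison is not established. A shift of about 0.2 to 0.9 days in mean ventilator-free days rests on an assumed excess of 2 to 5 points in one arm, 12 to 18 miscredited days each, and ventilation continuing to day 30. The direction could be either way. The matter concerns secondary outcomes only, and is worth correcting because the remedy is cheap.

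**What to change.** 1. In Secondary Outcomes (Clinical Metrics), let death from any cause by day 30 score 0 for all three measures, using the 1-month survival field already in Appendix B. State the day from which the 30 days run, and how a patient with unknown 1-month survival is handled.
2. Add to Appendix B a yes/no item for ventilation at discharge or transfer, taken from the index hospital record. Credit such patients with no further ventilator-free days to day 30 unless a liberation date is known: score = 30 - ventilator days - days from transfer to day 30. For patient 2 this is 30 - 14 - 16 = 0.
3. Report the scoring as now defined as a sensitivity analysis.
4. Optionally, add a sensitivity analysis of hospital-free days and length of stay in which transfer to an LTAC or another acute hospital does not end the stay.

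The cost is the wording of three definitions, one data item and one added analysis, or two with the optional one. The downside is that a few courses after transfer will be assumed rather than observed, and the assumption in item 2 is the opposite extreme to the present one; item 3 shows how much that matters. Sample size does not change.

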### Bayesian Analysis

Bayesian statistics will be used to detect differences in treatment effects overall and in different patient subgroups. Models will be the same as in frequentist analyses (*i.e.*, GLMs with same covariates). For LOS outcomes, neutral priors centered at RR of 1.0 with 95% prior interval of 0.33-3.0 (0.5-2 for binary outcomes) will be used for the treatment effect (in the log RR scale, a Normal distribution with mean of 0 and variance of 0.57). A Normal (0, 10) prior will be used for the intercept term. Normal (0, 1) will be used for all other variables in the model. For sensitivity analyses, we will specify enthusiastic and skeptical priors based on the best published evidence (*i.e.*, Cochrane review). For all Bayesian analyses, we will report posterior medians and 95% credible intervals for group comparisons and probabilities of benefit or harm from the intervention.

**Feasibility:** From unpublished historical data from the Red Duke Trauma Institute from the calendar year 2017, approximately 300 patients matched these enrollment criteria. Accordingly, enrollment of 150-250 patients is expected over the course of the study.

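### Re-intervention for surgical complications falls under the general two-arm relative-risk rule and its neutral prior, which suit a largely one-sided surgical harm poorly

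*Combined protocol and SAP*

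**What the plan says.** Under Secondary Outcomes (Clinical Metrics) the last item is "Re-intervention rates for surgical complications, including bleeding, seroma, and surgical site infection". No denominator, time window or expected rate is attached to it.

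Frequentist Analysis makes no exceptions: "Generalized linear models (GLMs) will be used to analyze all outcomes", with treatment group and unit of admission as covariates. For yes/no outcomes it adds: "Binary outcomes will be analyzed with log binomial regression models to estimate relative risks (RRs)". It closes with: "We will report RRs or group differences and 95% confidence intervals for all outcomes".

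Bayesian Analysis carries the rule over ("Models will be the same as in frequentist analyses") and sets "neutral priors centered at RR of 1.0 with 95% prior interval of 0.33-3.0 (0.5-2 for binary outcomes)" for the treatment effect.

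Three other places bear on who can have an event:

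- The Control Arm text under Randomization allows late SSRF in controls as salvage.
- Statistics specifies intention to treat, so events after salvage count in the control arm. A per-protocol analysis is also planned.
- Appendix B records seroma, hematoma, surgical site infection, hardware infection, hardware failure and hardware removal as post-SSRF items, for example "Post-SSRF seroma requiring intervention? (yes/no)".

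**The concern.** An RR model compares the risk of the same event in two groups that can both have it. Here one arm is assigned an operation and the other is not, and the data items that match the outcome exist only after that operation. The control risk is then close to zero by design. Two things follow.

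First, the frequentist RR has a denominator at or near zero. Second, the neutral prior states in advance that the two risks probably lie within a factor of two of each other, which is not a sensible starting belief for a complication of surgery that one arm mostly does not receive. With few events the prior dominates, and the headline quantities that the plan promises (posterior median, credible interval, probability of harm) would describe a surgical harm as close to neutral.

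**Working it through.** The documents give no re-intervention rate, salvage rate or power for this outcome, so there is no planned figure to reproduce. The event counts below are assumptions. Arm size is the plan's 75 per group (Sample Size Calculation). The unit-of-admission term is left out.

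**1. Frequentist RR with no control events.** RR = (x1/75)/(x0/75). With x0 = 0 it is infinite. Fitting the log-binomial model to 6/75 v 0/75 does not settle: the log RR drifts to 21.5 with a standard error of about 11,400.

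**2. Frequentist RR with one control event.** For 6/75 v 1/75, RR = 6.0. The standard error of log RR is √(1/6 − 1/75 + 1/1 − 1/75) = 1.068. The 95% CI is 6.0 × exp(±1.96 × 1.068) = 0.74 to 48.6. An estimate exists but says almost nothing.

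**3. How likely no control events are.** If control events arise only through salvage, P(none) = (1 − c·r)^n, where c is the share of controls given late SSRF and r the re-intervention risk after SSRF (both assumed).

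| c | r | 75 controls | 125 controls |
|---|---|---|---|
| 0% | any | 100% | 100% |
| 5% | 5% | 83% | 73% |
| 10% | 5% | 69% | 53% |
| 20% | 5% | 47% | 28% |
| 20% | 10% | 22% | 8% |

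**4. The prior.** A 95% interval of 0.5 to 2 gives a log-RR SD of ln 2/1.96 = 0.354 (variance 0.125).

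**5. The planned Bayesian result.** Grid posterior for the log-binomial model, log RR ~ Normal(0, SD 0.354), intercept Normal(0, SD 10), 75 per arm:

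| SSRF v control events | Observed RR | Posterior median RR (95% CrI) | P(RR > 1) |
|---|---|---|---|
| 4 v 0 | infinite | 1.25 (0.65 to 2.41) | 0.75 |
| 6 v 0 | infinite | 1.38 (0.73 to 2.62) | 0.84 |
| 12 v 0 | infinite | 1.79 (0.99 to 3.24) | 0.97 |
| 6 v 1 | 6.0 | 1.30 | 0.80 |

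In the 4 v 0 case the model puts the SSRF risk at 3.0% and the control risk at 2.4%, a gap of 0.6 points, although no control had an event.

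**6. Sensitivity.** The plan does not say whether the 10 in the intercept prior is a variance or an SD. Read as a variance, the 4 v 0 median is 1.23. With 125 per arm, 6 v 0 still gives 1.38 (intercept SD 10).

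**7. The same 4 v 0 data on the absolute scale.** SSRF: 4/75 = 5.3%, exact 95% CI 1.5% to 13.1%. Control: 0/75, exact upper limit 4.8%. Risk difference 5.3 points. A score-type interval built from the Wilson limits (2.1% to 12.9% for 4/75; 0% to 4.9% for 0/75) runs from 5.3 − √(3.2² + 4.9²) to 5.3 + √(7.6² + 0²), that is about −0.5 to 12.9 points. It is wide, but it is defined and it does not invent a control risk.

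**The case against.** Several points on the other side stand.

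- **Whose surgery counts is not stated.** The outcome is worded as surgical complications, not SSRF complications. Data Collection follows all subjects for surgical site infection and reoperation, and the plan expects concomitant injuries and more urgent procedures. A reader might infer that controls can have events only after salvage SSRF; the outcome text does not say that. The post-SSRF labels are supporting evidence, not proof: Appendix B also words its pneumonia items around SSRF, yet pneumonia is plainly a two-arm outcome.
- **The RR is not bound to fail.** A reader might conclude that it can never be estimated. That holds only with no control events. Salvage SSRF counted by intention to treat can supply some, and at high assumed rates with 125 controls the chance of none falls to 8%.
- **The RR route is inferred.** The item is called a rate and is not labelled binary, and the plan allows group differences as well as RRs. Still, the Appendix B fields are yes/no and binary outcomes are assigned to log-binomial RRs, so RR is the natural reading.
- **The size depends on the prior.** The section also states a variance of 0.57, apparently for length of stay. If that were used here, 4 v 0 would give RR 2.12 with P(harm) 0.89. Enthusiastic and skeptical priors are planned too, but as sensitivity analyses; the neutral prior leads.

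None of this removes the core. One control event does not cure the shrinkage (6 v 1 gives 1.30), and no text exempts the outcome or covers an arm with no events.

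**Conclusion.** The concern holds in a limited form. The general rule, read naturally, gives this outcome an RR that is undefined with no control events and very unstable with one or two. It also attaches a prior that reduces an assumed 4 to 12 events against none to an RR of about 1.25 to 1.79, with credible intervals that include 1.

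This rests on the outcome meaning mainly SSRF complications, on the binary prior of 0.5 to 2, and on illustrative event counts. A reader might go further and call this the trial's main surgical safety outcome. The documents set no safety hierarchy; it is one item in a list of secondary outcomes. The primary analysis of hospital length of stay is unaffected, so this is a modest correction.

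**What to change.** Add a short paragraph to the statistics section that:

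1. exempts this outcome from the log-binomial RR models and from the neutral RR prior;
2. states that it counts re-intervention for complications of SSRF;
3. reports the proportion with an exact 95% CI among all patients who underwent SSRF, with randomised SSRF and salvage SSRF shown separately;
4. reports counts by randomised arm and an absolute risk difference with an exact or score-type 95% CI, by intention to treat, so that the randomised comparison is kept.

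The cost is SAP wording only, and there is less modelling to do.
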